In Kenya, in large urban HIV Treatment Centers, children are seen in dedicated pediatric HIV clinics and transition to the separate adult HIV clinic at ~15-24 years of age. In other HIV Treatment Programs, children are seen on pediatric *days* with a team that may be identical or overlap considerably with the team providing care on separate adult care days. Finally, some clinics utilize the same team and days to offer care to children and adults, with a transition involved when a child no longer needs a caregiver/parent at visits and starts to receive independent care. In all scenarios, adult HIV care demands a higher level of autonomy and is associated with less specialized support than pediatric HIV care. **Well-conceived transitional models are needed because adolescents and young adults are a particularly vulnerable group. Adolescent HIV retention in care is lower than in adults, and adolescents have had increasing HIV-related mortality in contrast to declining mortality risk in adults.** This underscores the need for enhanced transitional care between pediatric and adult models of care.

In order for children to assume their own care, there must be accurate, well-conducted, and timely disclosure of their HIV status. However, in Kenya, we and others have noted that a large proportion of HIV-infected children have not been formally told they have HIV (disclosed) because of concerns of inadvertent disclosure to others, parental guilt regarding transmission, or concerns that the child will be unable to cope. Informing a child of any chronic illness is challenging because of a child's developmental limitations or because caregivers desire to protect children from negative consequences. However, delayed or poor disclosure practices can result in persistent mistrust of the health system. **Without disclosure, transition to adult HIV care cannot occur.** Disclosure to the child may also improve treatment adherence, physical health outcomes, and psychological adjustment to illness and family relationships. Programs are starting to address disclosure of HIV status to children, however, there are few systematic tools for disclosure and limited evaluation of impact of these tools. There is therefore an urgent need to develop interventions to assist HCWs with the challenging, but crucial process of HIV disclosure to children and adolescents.

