Approach: *We will randomize 20 clinics to receive the ATP or no intervention (SOC) and compare disclosure and appropriate transition using pre-specified milestones among a group of children and adolescents with heterogeneous ages. During early implementation, we will monitor fidelity to the intervention using modified plan-do-study-act (PDSA) cycles. We will track implementation outcomes and factors influencing implementation during the initial ATP implementation phase (6 months). During this time, the study team will discuss and support changes to refine the tool as needed at each facility. Following the initial implementation period, HCWs will take part in focus group discussions to share their suggestions for optimizing the transition tool based on their experience. Understanding personal experiences with the tool will provide an opportunity for lessons learned and continued refinement of the intervention. At the end of the study, we will qualitatively evaluate acceptability, appropriateness and feasibility of the ATP by conducting interviews and FGDs with all HCWs from implementing sites and adolescents from a sub-set of intervention sites, purposively selecting to include participants from high and low performing facilities. We will also conduct pre-trial and post-trial surveys with adolescents and HCWs to quantitatively assess acceptability, appropriateness, feasibility of the ATP and implementation intervention fidelity. At 6-monthly intervals, we will collect readiness assessment information from adolescents in participating clinics.*

SECTION 3: STUDY OUTCOMES

Aim 1

- Prevalence of transition
- Age at transition
- Co-factors for retention
- Age at disclosure
- Co-factors of disclosure
- Individual level co-factors of effective transition
- Facility level co-factors of effective transition

Aim 2

- Adapted transition tool

Aim 3

- The primary outcome is **disclosure** among non-disclosed adolescents and **effective transition and transition readiness** among disclosed adolescents

- Disclosure will be defined as no, partial or complete disclosure. Time to disclosure and age at disclosure will also be assessed.
- Effective transition with retention in care will be defined as completing a visit on the adult day or completing a visit without a caregiver and repeat visits continuing for at least 6 months after transition.
- Transition readiness will be defined as change in response to readiness assessment questions administered every 6 months

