All adolescents 15-24 years who have attained full disclosure and are attending clinic visits will be eligible to participate in the surveys. Adolescents will be recruited during clinic visits by a member of the study team or by phone prior to returning to clinic for their study visit. A recruitment script with guiding information is provided in the appendices. If an adolescent is interested in participating, eligibility will be assessed by clinic or study staff by asking adolescents a series of questions. These questions will confirm that the adolescent knows their HIV status and is within the appropriate age range to participate. Example questions that study staff might ask include: "why do you come to this clinic" and/or "why do you take medications" and "how old are you." Adolescents who meet eligibility criteria and are interested in participating will give written assent or consent to participate in the surveys. We will also request a waiver of parental permission for adolescents ages 15-17 who do not meet emancipated minor criteria. The information collected in the survey is not sensitive and can be classified as minimal risk. In addition, many adolescents ages 15-17 who have already attained full disclosure will be receiving care in the absence of their caregivers. Adolescents will be informed that their data will be linked to their medical record data, but this survey will not contain their name, only their ID. All adolescents who provide consent or assent will be enrolled and participate in this survey. Adolescents who provide assent or consent will take the transition readiness surveys every 6 months. Adolescents will receive 600 KES for completing the survey each time.

We will conduct disclosure readiness surveys at intervention sites with caregivers of children and adolescents aged 6-19 years who have not yet attained full disclosure. Surveys will be conducted at baseline (clinical trial start) and every 6 months thereafter until the study ends or the child/adolescent has reached full disclosure.

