All adolescents attending clinic visits will be eligible to participate in the anonymous surveys. Adolescents will be recruited during clinic visits by a member of the study team. A recruitment script with guiding information is provided in the appendices. If an adolescent is interested in participating, eligibility will be assessed by clinic staff by asking adolescents a series of questions. These questions will confirm that the adolescent knows their HIV status and is within the appropriate age range to participate. Example questions that study staff might ask include: “why do you come to this clinic” and/or “why do you take medications” and “how old are you.” Adolescents who meet eligibility criteria and are interested in participating will give oral assent or consent to participate in the anonymous surveys. A recruitment script with guiding information is provided in the appendices. They will be informed that no identifiable information will be collected in the surveys and that the study teams will not collect any names. All adolescents will provide oral assent or consent to participate in the surveys. Since no identifying information will be collected, we will request waiver of written consent for participation in the surveys. We will also request a waiver of obtaining parental consent for adolescents ages 12-17. We are looking at evaluating transition to adult care, and many adolescents ages 12-17 will have already transitioned to adult care and be receiving care in the absence of their caregivers. All adolescents who provide oral assent or consent will be enrolled and participate in an anonymous survey.

All HCWs working with HIV-infected adolescents at intervention sites are eligible to participate in exit surveys. HCWs who meet eligibility criteria will be recruited by study team members to participate. They will be informed that no identifiable information will be collected. It will be emphasized that participation is completely voluntary and opting not to participate will have no repercussions on the provider’s employment. All HCWs who provide oral consent will be enrolled and participate in an anonymous survey.

Data collection procedures

Pre and post-trial surveys will be collected either on paper CRFs or using mobile REDCap on tablets. These surveys are provided in the appendices. Data collected on paper forms will be entered into REDCap as described earlier.

List of procedures for pre and post-trial surveys

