- We assume that 100 of these eligible clients will be aged 6-15 and that the rate of complete disclosure will be 15% in the control clinics based on our prior studies and the literature with increased prevalence per year of age in this age-window.
- We assume that 100 of these eligible clients will be aged 15-24 years and that 20% (n=20) will be receiving care in a pediatric program and could be eligible to transition (200 per RCT arm). During 2-year follow-up, we anticipate that in the control arm 20% will transition and 10% will transition effectively.

With 10 intervention and 10 control sites, we will have sufficient power to detect an increase in proportion of adolescents with disclosure from 30% to 50%, an increase in proportion who initiate transition from 50% to >80%, and an increase in proportion with effective transition from 10% to 20%. This assumes alpha of 0.05, 80% power, and a conservative estimate of the coefficient of variation of 0.3 (Table 6). Heterogeneity between clusters is expected to decrease with control for baseline testing rates, leading to increased power beyond that which is noted above.

Table 8: Power and sample size ranges

	Outcome Control	Outcome Intervention	Number of clinics per RCT arm to detect difference
Age 10-15	N=1000 (100/clinic)	N=1000 (100/clinic)	
Disclosure process started (proportion)	50% 50% 50%	>80% >90% 100%	9 6 5
Disclosure complete (proportion)	30% 30% 30%	50% 70%	8 4 3
Disclosure age median	14 years old	12 years old	NA
24-month LTFU	20%	10%	7
Age 16-24	N=1000 (100/clinic)	N=1000 (100/clinic)	
Transition discussed (proportion)	20% 20% 50%	40% 60% 100%	6 3 5
Transition complete (proportion)	10%	20%	7
Transition satisfaction	50%	70%	NA
24-month LTFU	25%	15%	10

For the provider and adolescent IDIs, we will select healthcare providers and adolescents from ATP-implementing clinics for individual interviews. Clinics will be purposively selected from among all ATP-implementing clinics. We will purposively select clinics for interviews based on performance, including high and low performing sites as appropriate based on the outcome of the intervention. If the majority of clinics do well, we will purposively select a higher proportion of low performing clinics to understand why they had challenges. If the majority of the clinics do poorly, we will purposively select a higher proportion of high performing clinics to understand how they succeeded.

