Pre and post- trial surveys: We will request a waiver of written assent or consent for these participants. We will also request a waiver of parental permission for adolescents ages 12-17. As we will not be collecting any personal information, breach of confidentiality is of higher risk with written documentation rather than verbal agreement. We request waiver of parental consent because many adolescents attend the care clinic independently, without their caregivers. If caregivers are present with the child participant, we will respect caregivers' wishes if they do not want the child to complete the anonymous survey. Requirement of parental consent would be problematic for adolescents who have transitioned (eg, have assumed autonomy for their own care), and for those whose caregivers would be unavailable to come in and provide consent. Excluding these adolescents would bias the study population.

Transition readiness surveys: Written informed consent or assent will be sought from the adolescent ages 10-24 years. We will request a waiver of parental permission for adolescents ages 15-17 years because many adolescents present to clinic for care unaccompanied and the survey questions are minimal risk and ask about non-sensitive information. Requirement of parental consent would be problematic for adolescents 15-17 years who have attained full disclosure and potentially transitioned (e.g., have assumed autonomy for their own care), and for those whose caregivers would be unavailable to come in and provide consent. Excluding these adolescents would bias the study population.

Caregivers of HIV-infected adolescents

Caregivers will provide written informed consent.

Consent Details:

A consent form describing in detail the study procedures and risks will be provided. Participants will be informed that they are free to decline participation, and that declining to give permission will have no impact on their role in this study. Participants will be informed that they are free to withdraw their permission at any time during the study.

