- c. Self-management readiness score
- d. Communication readiness score
- e. Support readiness score

Analysis

Primary analysis ITT: Mixed effects linear regression to compare transition readiness scores (overall and by domain) over time in control and intervention sites with adjustment for multiple testing (Benjamin-Hochberg method).

Time points: Enrollment, month 6, month 12

Sample size and power table

Assumptions: 80% power, alpha 0.05, ICC 0.2, average cluster size of 50

Mean difference	SD	Number of Clusters per Arm
0.5	1	4
0.5	2	15
1.0	2	4
1.0	3	9
1.5	3	4
1.5	4	7
2.0	5	6
2.0	6	9

Secondary outcomes

- a. Overall retention in 10-24 year olds: defined as proportion of 10-24 year olds completing visits within 6 months of last visit
- b. Overall viral suppression: defined as proportion of 10-24 year olds with viral load of less than 1000 copies per ml after at least 6 months of ART

Analysis

Overall retention/suppression: Generalized estimating equations (GEE) to compare retention and viral suppression in intervention and control sites

Time-points: Baseline, month 6, month 12

Minimum detectable differences in proportions with outcomes

Assumption: 80% power, alpha 0.05, ICC 0.2, 10 clusters per arm, average cluster size of 50

Proportion with outcome in arm 1	Proportion with outcome in arm 2
0.2	0.31
0.3	0.44
0.4	0.56

0.5	0.69
0.6	0.81
0.7	0.93

Exploratory analyses

1. Post-transition retention defined as completing and adult clinic visit day after transfer to adult services and at least 1 other visit within 6 months of the adult visit (total of 2 visits):
Analysis: GEE to compare post-transition retention in intervention and control sites
2. Principal components analysis to identify the most representative components of data in the 4 domains of the readiness assessment checklist (HIV treatment literacy (Q 1-5), self-management (Q6, 7, 9-14, communication Q16-19, support 20-22) and then factor analysis to determine the most important components.
3. Proportion of children with full disclosure and time to full disclosure. Children who do not know their HIV status from HCW assessment. Child will be asked why they are taking medicine; if they report they have HIV they have reached full disclosure. If they mention any other illness or other responses they will not have reached full disclosure.
End point: Child says they have HIV in response to the question “why are you taking your medicine”
Analysis: Descriptive %, time to full disclosure

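### The protocol's effective transition outcome requires no change from baseline, so adolescents who already attend alone can count as successes in both arms and dilute the comparison

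*Combined protocol and SAP*

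**What the plan says.** Protocol Section 3 (Aim 3) lists effective transition within the primary outcome. Its definition reads "completing a visit on the adult day or completing a visit without a caregiver and repeat visits continuing", and the repeat visits must span no less than six months from the transition. Table 1 gives the proportion with effective transition, and age at and time to transition, for the group of disclosed adolescents, with no further restriction.

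Three consent passages describe the starting state of these adolescents:

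- Section 7c, on the readiness surveys: "many adolescents ages 15-17 who have already attained full disclosure will be receiving care in the absence of their caregivers".
- Section 7d, on the pre- and post-trial surveys: "many adolescents ages 12-17 will have already transitioned to adult care and be receiving care in the absence of their caregivers".
- Section 12a: "many adolescents attend the care clinic independently, without their caregivers".

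Section 11a assumes that, of 100 clients aged 15-24 per clinic, 20 are in a pediatric program and could be eligible to transition (200 per arm), and that 10% of controls will transition effectively over two years. Table 8 gives 7 clinics per arm for 10% v 20%, under a column heading of 100 per clinic.

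The SAP names transition readiness as its only primary endpoint. Its nearest outcome, post-transition retention, is exploratory. It needs an adult clinic visit "after transfer to adult services" plus one more visit within six months, has no caregiver route, and is marked in Appendix 1 as applying only in adolescent models of care.

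**The concern.** An outcome meant to show that a package moves adolescents into independent care should count people who move. The Section 3 rule has no condition on the earlier state, and it does not ask that the later visits also be unaccompanied. A disclosed 17-year-old who has always come alone to a pediatric clinic day can satisfy the caregiver route at the first trial visit and then only has to keep attending.

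If such youth are counted, they add the same successes to both arms. The arm difference shrinks, the control rate exceeds the 10% used for the sample size, and time to transition says nothing about the intervention for those youth.

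**Working it through.** **1. Definitions side by side.** In Section 2b, Aim 1 defines effective transition as a move: exit from pediatric care, enrolment in adult care within six months, then follow-up. The SAP's exploratory outcome also follows a transfer. Section 3 separately lists attendance without a caregiver as a behavioural indicator. Only the Aim 3 definition lets a visit without a caregiver qualify with no transfer stated.

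**2. The plan's own figure.** Inputs from Section 11a and Table 8: 10% v 20%, alpha 0.05 (two-sided assumed), 80% power, between-clinic coefficient of variation k = 0.3, m = 100 per clinic. The standard unmatched cluster formula (Hayes-Bennett) is

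c = 1 + (1.96 + 0.84)² × V / (p0 − p1)², with V = [p0(1−p0) + p1(1−p1)]/m + k²(p0² + p1²).

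V = 0.25/100 + 0.09 × 0.05 = 0.0070, so c = 1 + 7.849 × 0.0070/0.01 = 6.49, rounded up to 7. Table 8 is reproduced, but with 100 per clinic and not the 20 that Section 11a calls eligible. Ten clinics per arm would give 95% power.

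**3. Dilution if prevalent solo attenders are counted.** Let p be the share already attending alone, and let 80% of them stay in care. Both are assumptions: the documents give no p, and Table 8 uses 20-25% loss over 24 months in its control column. The remainder move at 10% or 20%.

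Rate = 0.8p + (1−p) × 0.10 (control) or × 0.20 (intervention), so the difference is 0.10 × (1−p).

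| p | Control | Intervention | Difference | Share of control successes who did not change |
|---|---|---|---|---|
| 10% | 0.08 + 0.09 = 17% | 0.08 + 0.18 = 26% | 9 points | 0.08/0.17 = 47% |
| 30% | 0.24 + 0.07 = 31% | 0.24 + 0.14 = 38% | 7 points | 0.24/0.31 = 77% |
| 60% | 0.48 + 0.04 = 52% | 0.48 + 0.08 = 56% | 4 points | 0.48/0.52 = 92% |

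Power with c = 10 is Φ(√[9(p0 − p1)²/V] − 1.96). It depends on how p varies between clinics, which is unknown. Keeping k = 0.3 on the diluted rates gives V = 0.0120, 0.0261 and 0.0575, and power 69%, 25% and 7%. If p is the same in every clinic, so that only the part still at risk varies (second term of V = (1−p)² × 0.0045), V = 0.0070, 0.0067 and 0.0057, and power is 90%, 73% and 36%.

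**4. After restricting to those at risk.** With m = 20 per clinic, V = 0.25/20 + 0.0045 = 0.0170 and c = 1 + 7.849 × 1.70 = 14.34, so 15 clinics per arm. Power with ten is Φ(√(0.09/0.0170) − 1.96) = Φ(0.34) = 63%. If half of those 20 already attend alone (assumption, m = 10), V = 0.0295, 25 clinics per arm are needed, and power with ten is 42%.

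**The case against.** The strongest reply is that the plan intends an at-risk reading. The definition runs to six months after transition, which presupposes an event. Section 10 describes a transition tracking log that is started at transition to adult clinics. Section 3 says achievement is judged within each adolescent's stage, as progression to independent care within the adult system. Section 11a ties the 10% control rate to clients still in a pediatric program. Section 11b adjusts for baseline transition proportions. The two-route rule also has a stated basis: Section 1a describes integrated clinics "with a transition involved when a child no longer needs a caregiver/parent at visits and starts to receive independent care", where no adult day exists to count.

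The last point stands in full, and the caregiver route should be kept for those clinics. The others show intent but do not close the gap. Progression within a stage is not a counting rule. The log presupposes a transition without saying when an unaccompanied visit is one. The Section 11a figure is a sample-size assumption, and being in a pediatric program does not exclude youth who already come alone. Covariate adjustment leaves them in the count.

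Three stronger readings are tempting, and the documents do not support them. A reader might infer that these youth will be counted; no text says so, only that nothing stops it. A reader might infer that the outcome mostly measures prior solo attendance; that needs a large p, and the documents say only that many attend alone, mainly about ages 12-17 or 15-17. A reader might infer bias toward one arm; that would need unequal baseline shares, and with balanced shares the effect is dilution.

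**Conclusion.** The concern holds as a gap in the definition. The Aim 3 rule sets no change-from-baseline condition and no at-risk denominator, in a population where the protocol says many already satisfy the caregiver route. The 10-point difference would shrink by the factor 1−p, to 9, 7 or 4 points at p = 10%, 30% or 60%. These values of p and the 80% staying in care are assumptions; the documents fix neither. Loss of information on time to transition is confined to the youth already attending alone.

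The reach is limited. A reader might conclude that the trial's main result is at risk, but the SAP's primary analysis is of readiness scores and does not use this outcome, and the SAP's exploratory retention outcome has no caregiver route. What is affected is the primary outcome as the protocol still states it, so the two documents need to agree on both its status and its definition.

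**What to change.** In protocol Section 3, with matching SAP text:

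- Restrict effective transition to disclosed adolescents who do not meet the criterion in the baseline data pull, in both arms.
- Count the first qualifying visit after baseline, by the clinic model recorded in the facility survey. Where a separate adult clinic or day exists, this is the first visit there. In same-day, same-team clinics, it is the first unaccompanied visit after an accompanied one, with the later qualifying visits also unaccompanied.
- Report youth who are already independent at baseline separately, and keep solo attendance as its own indicator.
- State whether effective transition is primary or exploratory, and use one definition in both documents.
- Restate the Table 8 row at the eligible cluster size.

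The cost is mainly wording. Baseline abstraction, clinic day, caregiver presence and clinic model are already planned data items. The drawbacks are a smaller denominator, dependence on how well caregiver presence is charted, and a less favourable stated power: about 63% with ten clinics per arm at 20 eligible per clinic, where 15 per arm would be needed, against the 7 in Table 8. The restriction exposes that shortfall; it follows from Section 11a's own eligible number.
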